7.3. Follow-up

7.3.1. Follow-up Visits, post first vaccination

Day 2 (V02), 3 (V03), 4 (V04) and 6 (V05)

Follow-up visits are scheduled in reference to study vaccination date as indicated for each visit window. All subjects will return on D2, 3, 4, 6 post the first vaccination. The following assessments will occur:

- Interim medical history will be obtained by interview of subjects to ensure continued eligibility. Any changes since the previous clinic visit or contact will be noted at each clinic visit.
- All concomitant medications (including solicitation for receipt of any non-study vaccines) will be recorded on the appropriate data collection form at each clinic visit. Any new concomitant medications taken since the last clinic visit or phone contact will be reviewed with subjects and assessed for continued eligibility.
- A targeted physical examination may be performed, if indicated based on review of complete medical history and any updates obtained by interview of subjects, by a study clinician licensed to make medical diagnoses and listed on the Form FDA 1572 as the site principal investigator or sub-investigator.
- Venous blood will be collected for immunogenicity and exploratory assays (please refer to [Appendix A](#): Schedule of Study Procedures and Evaluations for type of assays requiring collection).
- All AEs, SAEs and MAAEs will be collected and recorded on the appropriate data collection form at each clinic visit.
- Memory aid information will be reviewed with subjects at each clinic visit.

7.3.2. Follow-up Vaccination Visit

Day 8 +2 (post first vaccination), Visit 06

All subjects will return for vaccination on D8. The following assessments will occur.

- Eligibility criteria will be reviewed with subjects prior to study vaccination to ensure continued eligibility (see [Section 5.3](#)).
- Interim medical history will be obtained by interview of subjects to ensure continued eligibility. Any changes since the previous clinic visit or contact will be noted at each clinic visit.
- All concomitant medications (including solicitation for receipt of any non-study vaccines) will be recorded on the appropriate data collection form at each clinic visit. Any new concomitant medications taken since the last clinic visit or phone contact will be reviewed with subjects and assessed for continued eligibility.

- Vital signs, including oral temperature, pulse, and blood pressure, will be obtained to ensure continued eligibility. Subjects must not eat or drink anything hot or cold, or smoke within 10 minutes prior to taking oral temperature.
- A targeted physical examination may be performed prior to study vaccination, if indicated based on review of complete medical history and any updates obtained by interview of subjects since the screening visit, by a study clinician listed on the Form FDA 1572.
- A urine pregnancy test will be performed within 24 hours prior to study vaccination on all females of childbearing potential. Results must be negative and known prior to randomization and study vaccination.
- Venous blood will be collected prior to the study vaccination for safety labs (See [Section 8.2.1](#)).
- Venous blood will be collected prior to the study vaccination for future use assays.
- Venous blood will be collected prior to the study vaccination for immunogenicity and exploratory assays (please refer to [Appendix A](#): Schedule of Study Procedures and Evaluations for type of assays requiring collection).
- Pre-administration reactogenicity assessments will be performed prior to study vaccination to establish a baseline. Subjects will then receive study vaccine or placebo via intramuscular injection into the opposite arm that was used for the first injection (left or right deltoid). The time of administration will be recorded on the appropriate data collection form. Subjects will be observed for at least 30 minutes after study vaccination. Post-administration reactogenicity assessments will be performed. Any AEs, SAEs, and MAAEs will be recorded on the appropriate data collection form prior to discharge from the clinic.
- Subjects will be provided with a memory aid and other study-related materials to record daily oral temperature, solicited site and systemic AEs, unsolicited AEs, and concomitant medications. Subjects will be encouraged to take their oral temperature around the same time each day. Subjects must not eat or drink anything hot or cold, or smoke within 10 minutes prior to taking oral temperature. Subjects will be instructed on how to use their memory aid and how to measure and record AEs prior to discharge from the clinic. Subjects will be instructed to notify the study center if they develop any severe reactions after study vaccination. If the site principal investigator or appropriate sub-investigator deems the reaction severe enough, further instructions will be given to the subject on the proper course of action, including a return to the clinic for immediate evaluation if appropriate.
- All AEs, SAEs, and MAAEs will be collected and recorded on the appropriate data collection form at each clinic visit.

7.3.3. Follow-up Visits, post second vaccination

Day 2 (V07), 8 +1 (V08), 15 +2/-1 (V09), 22 +/-1 (V10), 29 +/-2 (V11) post second vaccination

Follow-up visits are scheduled in reference to study vaccination date as indicated for each visit window. All subjects will return on D2, 8, 15, 22 and 29 post the second vaccination. The following assessments will occur:

- Interim medical history will be obtained by interview of subjects to ensure continued eligibility. Any changes since the previous clinic visit or contact will be noted at each clinic visit.
- All concomitant medications (including solicitation for receipt of any non-study vaccines) will be recorded on the appropriate data collection form at each clinic visit. Any new concomitant medications taken since the last clinic visit or phone contact will be reviewed with subjects and assessed for continued eligibility.
- A targeted physical examination may be performed, if indicated based on review of complete medical history and any updates obtained by interview of subjects, by a study clinician listed on the Form FDA.
- Venous blood will be collected for immunogenicity and exploratory assays (please refer to [Appendix A](#) – Schedule of Study Procedures and Evaluations for type of assays requiring collection).
- Venous blood will be collected for safety labs only on Day 8 (+1), 22 (+/-1), and 29 (+/-2) post second vaccination (See [Section 8.2.1](#)).
- Venous blood will be collected for future use assays on Day 8 (+1), 15 (+2/-1), and 29 (+/-2) post second vaccination (See [Section 8.2.1](#)).
- All AEs, SAEs, and MAAEs will be collected and recorded on the appropriate data collection form at each clinic visit.
- Memory aid information will be reviewed with subjects on Day 2 and 8 post second vaccination.

7.3.4. Follow-up Phone Calls

Day 76 +/-7 (V12), Day 106 +/-7 (V13) post first vaccination

Follow-up visits are scheduled in reference to study vaccination date as indicated for each visit window. All subjects will be called at approximately D76 and 106 post the first vaccination. The following assessments will occur:

- Interim medical history will be reviewed to ensure continued eligibility. Any changes since the previous clinic visit or contact will be noted at the phone call.
- All SAEs and MAAEs will be collected and recorded on the appropriate data collection form at the phone call.

7.4. Final Study Visit

Day 182 +/-14 post first vaccination, Visit 14

Final visits are scheduled in reference to study vaccination date as indicated for each visit window. All subjects will return on D182 post the first vaccination for a final study visit. The following assessments will occur:

- Interim medical history will be obtained by interview of subjects. Any changes since the previous clinic visit or contact will be noted.
- A targeted physical examination may be performed, if indicated based on review of complete medical history and any updates obtained by interview of subjects, by a study clinician listed on the Form FDA 1572.
- Venous blood will be collected for future use assays.
- All SAEs and MAAEs will be collected and recorded on the appropriate data collection form.

7.5. Early Termination Visit (if needed)

The following activities will be performed on all subjects at the early termination visit on subjects who withdraw, or are withdrawn or terminated from this trial:

- Interim medical history will be obtained by interview of subjects and any changes since the previous clinic visit or contact will be noted (if indicated).
- Memory aid information will be reviewed with subjects (if within 7 days post study vaccination).
- All concomitant medications (including solicitation for receipt of any non-study vaccines) will be recorded on the appropriate data collection form (if prior to 28 days post second study vaccination).
- All AE, SAEs, and MAAEs will be recorded on the appropriate data collection form. AEs will be recorded if prior to 28 days post second study vaccination. AEs will be limited to SAEs and MAAEs, if after 28 days post first study vaccination.
- A targeted physical examination may be performed, if indicated based on review of interim medical history, by a study clinician licensed listed on the Form FDA 1572.

- Vital signs, including oral temperature, pulse, and blood pressure maybe obtained. Subjects must not eat or drink anything hot or cold, or smoke within 10 minutes prior to taking oral temperature.
- Venous blood will be collected for safety laboratory evaluations (see [Section 8.2.1](#)) and performed by the local (clinical) laboratory (if within 28 days post second study vaccination).
- Venous blood will be collected for immunogenicity and exploratory assays.

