3.2. Study Outcome Measures

3.2.1. Primary

- Frequency and severity of solicited local and systemic reactogenicity from the time of study vaccine administration through 7 days post-vaccination.
- Frequency and severity of vaccine-related unsolicited adverse events (AEs) from the first study vaccination through 28 days post second vaccination.

- Frequency and severity of clinical safety laboratory AEs from the time of first study vaccination through approximately 28 days after the second vaccination.
- Frequency of Serious Adverse Events (SAEs) and vaccine-related Medically Attended Adverse Events (MAAEs) through 6 months post first vaccination.

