7.6. Unscheduled Visit (if needed)

Unscheduled visits may occur at any time during this trial. Any of the following activities may be performed:

- Interim medical history will be obtained by interview of subjects and any changes since the previous clinic visit or contact will be noted (if indicated).
- Memory aid information will be reviewed with subjects (if within 7 days post study vaccination).
- All concomitant medications (including solicitation for receipt of any non-study vaccines) will be recorded on the appropriate data collection form (if prior to 28 days post second study vaccination).
- All AE, SAEs, and MAAEs will be recorded on the appropriate data collection form. AEs will be recorded if prior to 28 days post last study vaccination. AEs will be limited to SAEs and AEs if after 28 days post first study vaccination.
- A targeted physical examination may be performed, if indicated based on review of interim medical history, by a study clinician licensed listed on the Form FDA 1572.
- Vital signs, including oral temperature, pulse, and blood pressure, may be obtained. Subjects must not eat or drink anything hot or cold, or smoke within 10 minutes prior to taking oral temperature.
- Venous blood will be collected for safety laboratory evaluations (see [Section 8.2.1](#)) and performed by the local (clinical) laboratory (if within 28 days post second study vaccination).

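### Protocol Section 7.5 gives two end points for recording non-serious AEs, Day 29 and Day 36 to 38; the primary endpoint supports only the later one, and Section 7.6 has a related slip

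*Protocol*

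**What the plan says.** Protocol Section 3.2.1 defines the relevant primary outcome as "Frequency and severity of vaccine-related unsolicited adverse events (AEs) from the first study vaccination through 28 days post second vaccination". Sections 4, 9.1, 9.3, 9.4 and 11.4.2 use the same end point, as do SAP Sections 3.2.1, 4.5.1 and 9.3.2.

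For the early termination visit, Section 7.5 opens consistently with this: "AEs will be recorded if prior to 28 days post second study vaccination". The next sentence changes the anchor: "AEs will be limited to SAEs and MAAEs, if after 28 days post first study vaccination".

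For the unscheduled visit, Section 7.6 has a similar pair. First: "AEs will be recorded if prior to 28 days post last study vaccination". Then: "AEs will be limited to SAEs and AEs if after 28 days post first study vaccination". The restricted list there is SAEs and AEs, where Section 7.5 has SAEs and MAAEs.

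At the scheduled post-boost visits (Section 7.3.3) there is no such restriction: "All AEs, SAEs, and MAAEs will be collected and recorded on the appropriate data collection form at each clinic visit".

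**The concern.** All three arms receive the same first injection, so they differ only after the boost. Every day on which the two sentences of Section 7.5 disagree is a post-boost day.

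A subject who terminates early has no later visit at which an unrecorded event could be picked up. The analysis would not reveal the omission either. SAP Section 9 uses the safety population as denominator (or those who received the dose, for by-dose results), and SAP Section 6.5 imputes nothing, so an AE that was never recorded counts as no event. With 20 subjects per arm, one subject is 1/20 = 5 percentage points of incidence. The halting rule in Protocol Section 9.5 for repeated related grade 3 unsolicited AEs draws on the same records.

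**Working it through.** **Inputs**
- Day of first vaccination: Day 1.
- Day of boost: "Day 8 +2 (post first vaccination), Visit 06" (Section 7.3.2), so Day 8, 9 or 10.
- Post-boost visits: "Day 2 (V07), 8 +1 (V08), 15 +2/-1 (V09), 22 +/-1 (V10), 29 +/-2 (V11) post second vaccination" (Section 7.3.3).
- Endpoint limit: 28 days after the second vaccination (Section 3.2.1).
- Limit in the second sentence of Section 7.5: 28 days after the first vaccination.

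**Reproducing the schedule.** Appendix A places V11 on Day 29 counted from the second vaccine and Day 36 counted from the first. With a Day 8 boost, 8 + 29 - 1 = 36, which agrees. It also equals 8 + 28, so V11 falls on the nominal last day of the endpoint window.

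**The two limits.** The limit from the first vaccination is 1 + 28 = Day 29. The limit from the second is boost day + 28.

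| Boost day | 28 days after first | 28 days after second | Gap | Share of 28 post-boost days |
|---|---|---|---|---|
| 8 | Day 29 | Day 36 | 7 | 7/28 = 25.0% |
| 9 | Day 29 | Day 37 | 8 | 8/28 = 28.6% |
| 10 | Day 29 | Day 38 | 9 | 9/28 = 32.1% |

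The gap is measured to the end of the endpoint window. If both sentences were anchored to the second vaccination, it would be 0.

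**What one subject could lose.** Suppose the restriction is applied by date of AE onset. For an early termination visit inside the window on study Day d, the days at risk are d - 29, and none if d is 29 or earlier. A visit on Day 32 puts 32 - 29 = 3 days at risk. The full gap arises only for a visit at or after the end of the window, with V11 missed.

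The 9-day figure also assumes that V10 contributed nothing. With a Day 10 boost, V10 falls on 10 + 22 - 1 = Day 31, plus or minus 1, and collects all AEs. If V10 was attended, the stretch left before Day 38 is 38 - 31 = 7 days (6 to 8 with the visit window).

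Section 7.5 does not say whether its limit refers to AE onset or to the visit date. On the visit-date reading, a subject who had missed V09 and V10 could lose non-serious AEs back to the last contact, which is more than 7 days. The documents do not settle which reading applies.

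**Section 7.6.** A restriction to SAEs and AEs removes no AE, so the second sentence takes nothing away as written. A subject who stays on study after an unscheduled visit is asked about all AEs again at V11.

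**The case against.** The strongest reply is that this is a drafting slip against a clear governing rule. The sentence immediately before the disputed one in Section 7.5 gives the endpoint's limit, and so do Sections 3.2.1, 4, 9.1, 9.3 and 9.4. Within Sections 7.5 and 7.6, concomitant medications and safety laboratory tests are also tied to the second vaccination. Section 9.2.4 makes the investigator responsible for recording all AEs observed or reported during the trial. A site reading the whole protocol would probably use the later limit. For a subject who never received a second dose, a limit counted from the first vaccination is not even wrong.

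The group at risk is also narrow. SAEs and MAAEs are retained under either sentence. Section 9.2.1 defines medical attention broadly enough that an AE prompting an unscheduled visit is arguably an MAAE. The endpoint counts only vaccine-related events, and the disputed days begin about three weeks after the boost (29 - 8 = 21 days). Section 11.4.5 expects little missing data.

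All of this stands, and it limits the size of the point. It does not remove the contradiction: two adjacent operative sentences give a site different instructions for the same visit, on data that feed a primary safety endpoint.

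A reader might go further and infer that non-serious AE recording stops at Day 29 at both visit types, so that a quarter or more of post-boost follow-up is lost there. The documents do not support that. Section 7.5 contradicts itself rather than imposing a clear stop, Section 7.6 excludes nothing as written, and subjects who remain in the trial are covered by V11.

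**Conclusion.** The point holds as an internal contradiction in the data-collection instructions. Section 7.5 disagrees with itself, and with Sections 3.2.1, 9.3 and 9.4, on when recording of non-serious AEs ends. The conflict covers 7 days for an on-schedule Day 8 boost and up to 9 days for a Day 10 boost, or 25% to 32% of the 28 post-boost days.

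Those percentages are not an estimate of missing data. A loss requires all of the following: the subject terminates early after Day 29; the AE is neither serious nor medically attended; no other visit captured it; and the site followed the second sentence rather than the first. The documents give no count of such subjects, and it is probably small. For Section 7.6 no loss is shown; the defect there is a mismatched anchor and a garbled list.

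The point is worth correcting because it touches how a primary endpoint is collected and costs almost nothing to put right. No planned statistical method is affected.

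**What to change.** In Sections 7.5 and 7.6, anchor the restriction to the second study vaccination, or to the last one received if no second dose was given. This matches the primary endpoint and the last-vaccination wording already in Section 7.6. In Section 7.6, change the restricted list from SAEs and AEs to SAEs and MAAEs. State in both places whether the limit refers to AE onset or to the visit date, and align the eCRF guidance. The cost is a few words, with no added visits or samples.

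Parts of the SAP are written in the past tense, so data collection may be over. In that case the sponsor should confirm with the site which limit was applied at early termination visits after Day 29, and state it in the CSR together with the number of such visits. The SAP Preface already provides for describing deviations there.

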7.6. Unscheduled Visit (if needed)

Unscheduled visits may occur at any time during this trial. Any of the following activities may be performed:

- Interim medical history will be obtained by interview of subjects and any changes since the previous clinic visit or contact will be noted (if indicated).
- Memory aid information will be reviewed with subjects (if within 7 days post study vaccination).
- All concomitant medications (including solicitation for receipt of any non-study vaccines) will be recorded on the appropriate data collection form (if prior to 28 days post second study vaccination).
- All AE, SAEs, and MAAEs will be recorded on the appropriate data collection form. AEs will be recorded if prior to 28 days post last study vaccination. AEs will be limited to SAEs and AEs if after 28 days post first study vaccination.
- A targeted physical examination may be performed, if indicated based on review of interim medical history, by a study clinician licensed listed on the Form FDA 1572.
- Vital signs, including oral temperature, pulse, and blood pressure, may be obtained. Subjects must not eat or drink anything hot or cold, or smoke within 10 minutes prior to taking oral temperature.
- Venous blood will be collected for safety laboratory evaluations (see [Section 8.2.1](#)) and performed by the local (clinical) laboratory (if within 28 days post second study vaccination).

8 STUDY PROCEDURES/EVALUATIONS

8.1. Clinical Evaluations

Complete medical history will be obtained by interview of subjects at the screening visit and will be reviewed and/or updated on Day 1 prior to study vaccination. Subjects will be queried regarding a history of significant medical disorders of the head, eyes, ears, nose, throat, mouth, cardiovascular system, lungs, gastrointestinal tract, liver, pancreas, kidney, urologic system, nervous system, blood, lymph nodes, endocrine system, musculoskeletal system, skin, and genital/reproductive tract. A history of any allergies, cancer, immunodeficiency, psychiatric illness, substance abuse, and autoimmune disease will be solicited. At follow-up visits after study vaccination, an interim medical history will be obtained by interview of subjects noting any changes since the previous clinic visit or contact. The interim medical history should include an assessment for new medical conditions.

Medication history (concomitant medications) will include a review of all current medications and medications taken within 60 days prior to signing the informed consent form through approximately 28 days after the second study vaccination or early termination (if prior to 28 days after the second study vaccination), whichever occurs first. Medications reported in the eCRF are limited to those taken within 30 days prior to study vaccination through approximately 28 days after the second study vaccination. Prescription and over-the-counter drugs will be included as well as herbals, vitamins, and supplements. In addition, receipt of non-study vaccines will be solicited through approximately 28 days after the second study vaccination, and reported in the eCRF. Use of new medication should prompt evaluation for the occurrence of any AE. Assessment of eligibility will include a review of all permitted and prohibited medications per the Subject Inclusion and Exclusion Criteria (see [Sections 5.1](#) and [5.2](#)). In addition, the site principal investigator or appropriate sub-investigator may identify other medications that should not be used due to a risk to subject safety or assessment of reactogenicity and immunogenicity.

A full physical examination will be performed on all subjects at the screening visit. This exam will include the following organs and organ systems: skin, head and neck, lungs, heart, liver, spleen, extremities, musculoskeletal, lymph nodes and nervous system, by a study clinician licensed to make medical diagnoses and listed on the Form FDA 1572 as the site principal investigator or sub-investigator. Vital signs (oral temperature, pulse, and blood pressure) will be collected at the screening visit. Subjects must not eat or drink anything hot or cold, or smoke within 10 minutes prior to taking oral temperature. Height and weight will be collected at the screening visit. BMI will be calculated, and eligibility determined.

A single, 12-lead ECG will be performed at screening and will be read locally. Electrocardiograms will only be repeated during the study if clinically indicated based on signs and symptoms (per the investigator's judgment). During the collection of ECGs, subjects should

be in supine position in a quiet setting without distractions. Subjects should rest (while sitting comfortably) for at least 5 minutes before ECG collection and should refrain from talking or moving arms or legs.

On Day 1 prior to the study vaccination and at follow-up visits after the study vaccination, a targeted physical examination may be performed, if indicated based on the subject's interim medical history, by a study clinician licensed to make medical diagnoses and listed on the Form FDA 1572 as the site principal investigator or sub-investigator.

On Day 1 and all vaccination visits, vital signs (oral temperature, pulse, and blood pressure) will be collected prior to study vaccination. A urine pregnancy test will be performed within 24 hours prior to study vaccination on all females of childbearing potential. Pre-administration reactogenicity assessments will be performed prior to each study vaccination to establish baseline, then the study vaccination will be given. Subjects will be observed in the clinic for at least 30 minutes after each study vaccination. The study vaccination site will be examined, post-administration reactogenicity assessments will be performed and any AE, SAEs and MAAEs will be recorded on the appropriate data collection form prior to discharge from the clinic. All subjects will receive and complete a subject memory aid from the time of study vaccination through 7 days after study vaccination. Subject memory aids will be reviewed with the subjects for adverse events, (solicited local and systemic AEs and unsolicited AEs) approximately at day 8 after each vaccination.

Reactogenicity assessments will include an assessment of solicited adverse events occurring from the time of study vaccination through 7 days after study vaccination. These include local reactions such as pain, tenderness, erythema (redness), induration (hardness/swelling), pruritic (itching) and bruising as well as systemic AEs such as fever, feverishness (chills, shivering, sweating), fatigue (tiredness), malaise (general unwell feeling), myalgia (body aches/muscular pain), nausea, loss of appetite and headache.

